2.5 What are the planned inclusion/exclusion criteria?

Inclusion Criteria. Eligibility will be based on elevated scores on the Autism Parent Screen for Infants (APSI³⁷) supported by expert clinician impression of red flags for autism spectrum disorder (ASD), or a confirmed diagnosis of ASD made by a qualified professional (parents will be asked to provide the clinical report). Toddlers will be between ages 12 and 42 months at enrollment, having been born between 36 and 42 weeks’ gestation, with birthweight $>2,500$ g and no neurological, genetic, or severe sensory or motor conditions. Participating families must be residing in Ontario, Nova Scotia, or Alberta at the time of participation.

Requirements for participation include ability to comprehend verbal English instructions. Our Parent Training Manual is written at a grade four language level, but concepts are shared verbally and through images, so literacy is not a requirement. Participation is also dependent on access to high-speed internet and willingness to be video-recorded, for cross-site consistency checks and data acquisition. Parents will be asked to limit other social communication intervention programs (e.g., through Speech-Language Pathology, Occupational Therapy, Applied Behaviour Analysis, or related services) to 1 hour per week. Parents will also complete weekly services log to document involvement in such programs. Finally, parents will be encouraged to try not to miss more than 2 sessions in a row. Missed sessions will be rescheduled if possible. However, all families will be invited to provide end-of-study data even if multiple sessions are missed (number of sessions attended will be used as a covariate in analyses). Families may withdraw at any time.

There are no ***exclusion criteria*** other than failure to meet inclusion criteria.

2.6 Proposed duration of treatment period.

Treatment duration is 6 weeks. Time span between data collection time points will range from 7 to 9 weeks to allow for re-scheduling if necessary.

2.7 Proposed frequency and duration of follow up.

Data will be collected for both groups at: baseline (*Time 0*), 6 weeks later (*Time 1; within 6-8 weeks*), and following the next 6 weeks (*Time 2; within next 6-8 weeks*). Time 2 for the treatment group provides follow-up data to examine maintenance of gains in our primary outcome (toddler vocal responsiveness) and parent fidelity.

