2.9 How will the outcome measures be measured at follow up?

Primary Outcome: Toddler vocal responsiveness. Consistent with our previous work^{21,22}, video coding will be used to measure toddlers' vocal responsiveness (proportion of appropriate child vocal responses following a caregiver prompt, from 10-minute video). All video coding will be conducted by blinded research staff with established reliability, per established protocols. *The primary outcome is change in toddler vocal responsiveness from time 0 to time 1.*

***For all parent-child interaction videos**, parents are instructed to: “*play with your child as you typically play*” and reminded that: “*we want to see both of you on the screen as much as possible*”. **Two 10-minute video clips** will be collected and coded per time point (using average per time-point for analyses); **no coaching occurs during data videos**. Videos will be collected by research staff over the virtual platform, saved to virtual drives within institutional firewalls, and shared securely for coding, based on formal data-sharing agreements. **Blinded research staff with established inter-rater reliability will code all videos, per established protocols.**

Secondary Outcomes (all measures used in our previous and/or ongoing work):

1. *Toddlers.* (a) Vocal initiations and (b) social orienting (both blind-coded from video); (c) parent-rated word inventory (MacArthur-Bates Communicative Development Inventory [CDI]³⁸); (d) autism symptoms (APSI³⁷). 2. *Parents.* (a) Correct use of *Social ABCs* strategies (%)

implementation fidelity from blind-coded video), (b) self-efficacy (Parent Self-Efficacy Scale²² developed for our previous work), (c) parenting stress (Parenting Stress Index-4-Short Form³⁹).

Exploratory Analyses:

1. **Predictor variables:** Continuous (parenting stress, child age, baseline word inventory, ASD symptoms) and categorical (toddler sex, parent gender, parenting role, educational attainment, employment, ethnicity, English spoken at home, family structure), variables (collected from the *Family Profile Form*²⁴) will be assessed for their effect on the outcomes;

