2.16 What is the proposed type of analyses?

The primary analysis will yield a comparison of rates of toddler vocal responsiveness between the two conditions, controlling for the variables described above. The statistical model for the

Primary Outcome will be either a Poisson or negative binomial regression (if there is overdispersion of the counts), using the number of prompts and/or time as offsets and applying the appropriate correlation structure for observations by participant, and controlling for intraclass correlation due to clustering. Growth curve analysis will be used to calculate the trajectory of change in responsive vocalizations over time for each person based on whatever data are available (if at least 2 measurements), and then estimates (imputes) the missing data if the person followed the same trajectory. Otherwise, a worst-case (no vocal response) scenario can be used.

Secondary Outcomes: We will analyze as per the primary outcome for count variables (e.g., video-coded toddler initiations). We will use repeated measures ANOVA or Generalized Estimating Equations for scores (e.g., word inventory, ASD symptoms, parent efficacy, stress).

Exploratory Analyses: (1) *Predictors* of primary and secondary outcomes will first be assessed univariately for their effect on the outcomes, and significant factors will be subjected to multivariate analysis using the appropriate regression model. We will examine the influence of sex (toddlers), parent gender, and parenting roles by entering these factors as covariates. Given that sample size calculations are not done for all these factors, these analyses are exploratory. (2) *Implementation metrics* (feasibility, acceptability) will be examined descriptively.

[figure not shown]
2.17 Proposed frequency of analyses. Analyses will be conducted at two time points: (1) following the end of Phase 1 ($n = 30$), and (2) at the end of the larger trial ($n = 100$).

2.18 Planned subgroup analyses.

Subgroup analyses, run separately for treatment and control groups, will explore effects of: (1) sex: *Do outcomes differ for boy vs. girl toddlers?*; (2) gender: *Are there differences in parent fidelity and self-efficacy based on self-identified parent gender?*; (3) baseline language functioning: *Do outcomes differ for toddlers who begin the program below (vs. at or above) a 12-month language level (based on parent-reported CDI scores)?*

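### The primary comparison adjusts for covariates named only by a back-reference, and neither set of variables it could mean suits a confirmatory model

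*Protocol*

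**What the plan says.** The first sentence of Protocol Section 2.16 states that the two conditions will be compared on the primary outcome "controlling for the variables described above". The section lists no covariate for that model. It gives the model family (Poisson or negative binomial with an offset), a correlation structure within participant, and allowance for clustering.

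The text before Section 2.16 offers two candidates:

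- Section 2.9, under its exploratory heading, lists 12 predictor variables. Four of them are given as "Continuous (parenting stress, child age, baseline word inventory, ASD symptoms". The other eight cover the child's sex, the parent's gender and role, education, employment, ethnicity, home language and family structure, and are treated as categorical.
- Section 2.5 says the "number of sessions attended will be used as a covariate in analyses". This is the only variable before Section 2.16 that is expressly called a covariate, and the analyses concerned are not specified.

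Later in Section 2.16 the predictors have a paragraph of their own. They are screened one at a time, and then the "significant factors will be subjected to multivariate analysis using the appropriate regression model". Toddler sex, parent gender and parenting role are examined "by entering these factors as covariates". The paragraph ends: "Given that sample size calculations are not done for all these factors, these analyses are exploratory".

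**The concern.** The covariates of a primary model should be fixed before data are seen, because the estimate and its standard error depend on them. Here the protocol commits to adjustment, but the set is whatever a later analyst decides was described above. This goes beyond a detail left open for the analysis plan, since any analysis plan would have to reconcile its own list with this sentence and with Section 2.5.

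The two candidates fail in different ways. The predictors come largely from questionnaires and a family form, they were not allowed for in the sample size, and blank items could drop families from the primary analysis. The session count is a consequence of allocation, so conditioning on it changes the question the trial asks.

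**Working it through.** **Inputs.** Analysed n = 100, about 50 per arm, 80% power, alpha .05, a medium effect with no number attached (Section 2.10); an early analysis at n = 30 (Section 2.17); 12 predictors (Section 2.9); six didactic plus nine coaching sessions in Arm A and three group sessions in Arm B (Section 2.2). Category counts for the 8 categorical predictors are not given, so 20 and 25 parameters are assumed as a range above the minimum of 12.

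**Step 1: the plan's own power figure.** Take a medium effect as 0.5 SD (assumed).

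- Two-sided: Φ(0.5 × √(50/2) − 1.96) = Φ(0.54) = 70.5% (t test: 69.7%).
- One-sided: Φ(2.5 − 1.645) = Φ(0.855) = 80.4%.
- Overall F test in a regression with f² = 0.15 and N = 100: 81.3% with 6 predictors, 78.5% with 7, 66.0% with 12.

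The stated 80% is reproduced by a one-sided test, or by an overall test with 6 or 7 predictors. The protocol does not say which was used, so the power statement does not identify the covariate set.

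**Step 2: reading (a), the 12 predictors.** In a linear approximation, k covariates unrelated to arm or outcome multiply the variance of the treatment effect by (n − 3)/(n − 3 − k). If they explain a share R² of the outcome variance, the multiplier becomes (1 − R²) × (n − 3)/(n − 3 − k).

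The second power column starts from the stated 80%: Φ(2.80/√multiplier − 1.96). The last three use the two-sided t test at 0.5 SD.

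| k | Multiplier, no information | From stated 80% | R² = 0 | R² = 0.20 | R² = 0.43 |
|---|---|---|---|---|---|
| 0 | 1.00 | 80% | 69.7% | – | – |
| 12 | 97/85 = 1.14 | 75% | 63.8% | 73.5% | 86.5% |
| 20 | 97/77 = 1.26 | 70% | 59.5% | 69.1% | 83.0% |
| 25 | 97/72 = 1.35 | 67% | 56.6% | 66.1% | 80.4% |

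The R² values are assumptions. The 0.43 borrows the figure Section 2.10 reports from the previous RCT, as an illustration only. Setting (1 − R²) × 97/(97 − k) = 1 gives the break-even point R² = k/97, which is 12%, 21% and 26% for 12, 20 and 25 parameters. Below it adjustment costs precision; above it adjustment gains. At n = 30 with k = 12 the multiplier is 27/15 = 1.80.

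**Step 3: stress and ASD symptoms within reading (a).** Both are also secondary outcomes (Section 2.8). In the Section 2.9 list only word inventory carries the word baseline. The virtual pilot in Section 2.19 reports symptom scores falling from 23.2 to 18.5 and a trend in stress from 31.8 to 25.5. If post-treatment values entered the model, part of the treatment effect could be adjusted away.

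**Step 4: reading (b), sessions attended.** Arm A schedules 6 + 9 = 15 sessions and Arm B 3. With full attendance, sessions = 3 + 12 × arm, so the covariate is arm itself and the treatment effect cannot be estimated. With missed sessions, let s be the within-arm SD (assumed). At 1:1 allocation the between-arm variance is 12² × ¼ = 36, so the variance of the arm coefficient is multiplied by 1 + 36/s²: 37, 10 and 5 for s = 1, 2 and 3. The coefficient also changes meaning. It would compare arms at equal session counts, although Arm B cannot exceed 3.

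**The case against.** A reader might infer that the protocol puts all 12 predictors into the primary model, and so overfits it and contradicts itself. The documents do not support that. No sentence makes the 12 predictors covariates of the primary model, and screening them one at a time in a separate exploratory paragraph would make little sense if all were already forced in. The contradiction exists only if that reading is the one intended.

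Overfitting is also too strong at n = 100. With 12 parameters plus intercept and arm there are 100/14 = 7.1 toddlers per coefficient, and the model is estimable. The power losses in the R² = 0 column assume pure noise, whereas child age and word inventory may well be prognostic.

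Nor is a large rise in false positives established. A simulation with normal scores and uncorrected group-robust z tests gave 10–15% with 20–25 covariate parameters, against 7–10% with arm only. A clustered Poisson check nearer to the planned model (about 18 groups, 600 runs, assumed variances) gave 6.8%, 9.2% and 8.7% with 0, 12 and 20 covariates, with Monte Carlo error of about 1 point. Much of the excess comes from having few groups, and the protocol names no uncorrected estimator.

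Three further points are fair. Time 0 responsiveness may already be in the model as a repeated observation, so its absence from the predictor list is not in itself a defect. Nothing says post-treatment stress or symptom scores would be used. The session-count sentence may have been meant for compliance analyses only.

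A full covariate list is commonly left to the analysis plan, but that does not answer the point. The protocol makes a positive commitment whose object cannot be identified, and Section 2.5 applies its covariate to analyses without restriction.

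**Conclusion.** The point holds as a defect of specification: the adjustment set of the primary model is undefined, and neither available referent is suitable.

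Under reading (a) the cost is moderate and conditional: about 14% more variance at 12 parameters and n = 100 if the predictors are uninformative, more if categorical factors take several parameters, and a possible gain if together they explain more than about 12% of the outcome variance (at 12 parameters). Under reading (b) the damage is to the estimand as well as to precision, because the covariate follows from allocation and is nearly determined by arm.

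The figures rest on a linear approximation to a count model, assumed parameter counts, and an assumed spread of attendance. The conclusion that the sentence needs replacing does not depend on them. It should be changed before analysis, including the planned n = 30 analysis.

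**What to change.** In Section 2.16, replace the back-reference with a short fixed list of covariates measured before allocation: Time 0 vocal responsiveness (unless Time 0 is already modelled as a repeated observation), child age, Time 0 word inventory, and any factor used to stratify randomisation. Section 2.3 names no such factor at present.

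Add that the remaining Section 2.9 predictors, at Time 0 values, enter only the exploratory analyses. Amend Section 2.5 so that sessions attended is used only in exploratory or compliance analyses and never in the primary arm comparison.

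This takes a few sentences across two sections and needs no new data. The one loss is adjustment for the other predictors, some of which might be mildly prognostic.

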2.1 What is the trial design?

This is a multi-site, single-blind, randomized group treatment trial. Participants are subjected to three design components (further detailed below): (1) parallel group design with a treatment and an active control arm, (2) own-control (within subject) design for the control arm after these

participants receive treatment (control-treatment), and (3) growth curve analysis of treatment group at *Time 0* (baseline), *Time 1* (after treatment), and *Time 2* (follow-up).

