2. **Implementation metrics.** We will measure *acceptability* using our post-treatment Parent Satisfaction Scale²², and a Coaches' Satisfaction Scale (under development) to capture Coaches' perceptions of the adapted model relative to the standard approach. Program *quality metrics* will include evaluation of Coaches' fidelity (based on pre-established video-coding methods). We will examine *participant flow* metrics such as referral sources, ages of children, and number referred, eligible, enrolled, and completed, as well as number of sessions attended/missed/rescheduled.
2. **Sub-group and predictor analyses** will explore child factors (e.g., age, sex, baseline language level) and family factors that are facilitators or barriers to treatment uptake and successful outcomes (e.g., parents' educational attainment, current employment, family structure, parent gender)⁴⁰, using data collected from a Family Profile Form used in our previous work²².
3. **Follow-up (treatment group only).** A 10-minute parent-child interaction video will be collected and coded for toddler responsiveness and parent implementation fidelity using the same procedures as for *time 1* and *time 2*.

2.10 Proposed sample size and justification for assumptions underlying power calculations.

We aim to enroll 120 families into the RCT, across the three participating sites.

This project has two phases, differing only by number of participants and funding source. Specifically, phase 1 (funded by Kids Brain Health Network) involves enrollment of 30 families across the 3 participating sites. For phase 2, funds are being sought through CIHR (to be adjudicated in March 2021). If funded, we will submit an amendment to increase recruitment up to 100. The proposed sample ($n = 100$; ~50 per treatment arm) will yield 80% power to detect a medium effect (at alpha = .05)⁴¹. The assumption of a medium effect comes from our previous RCT which yielded $R^2 = .43$ for the same primary outcome²². We will over-sample by 20% (i.e., recruit to $n = 120$) to allow for attrition (see 2.14). Given that this is an individually randomized group treatment trial (with 1 group-based and 1 individually administered arm) analyses will account for the intra-class correlations associated with group participation, as recommended³⁴. If Phase 2 is not funded, we will use data from Phase 1 as pilot data for further funding applications.

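### Setting missing responsiveness to zero is worst-case for a toddler but not for the between-arm comparison, and the trajectory step can carry post-program data into a control's Time 1

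*Protocol*

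**What the plan says.** Section 2.9 of the Protocol fixes the endpoint: "The primary outcome is change in toddler vocal responsiveness from time 0 to time 1". Section 2.16 makes the primary analysis a comparison of response rates between the two conditions, by Poisson or negative binomial regression with an offset.

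Section 2.16 then handles missing values in two steps. A growth curve is calculated for each participant, "based on whatever data are available (if at least 2 measurements", and the method "estimates (imputes) the missing data if the person followed the same trajectory". Where that is not possible, "Otherwise, a worst-case (no vocal response) scenario can be used". Neither step names an arm, and the text does not say whether the zero belongs to the primary or to a sensitivity analysis.

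Four other places bear on this:
- Section 2.2: the Time 0 video is taken before the allocation is revealed, and Arm B families are offered the program once the control phase ends.
- Section 2.1: controls then serve as their own comparison after treatment.
- Section 2.7: "Data will be collected for both groups at: baseline", Time 1 and Time 2.
- Section 2.14: retention of 85-90% is expected; the previous RCT kept 90.3% of treatment and 93.8% of control families at 6 months.

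**The concern.** The label worst-case invites the reader to treat the zero-imputed result as a floor: if the effect survives it, missing data cannot explain the effect. That holds for zeros in Arm A. It fails for zeros in Arm B, where each one lowers the control mean and widens the difference. The direction of the bias then depends on which arm loses more families.

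The rule would have cases to act on. Because Time 0 precedes disclosure of allocation, a family lost before Time 1 normally has one measurement, fails the two-measurement condition and falls to the zero rule.

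The trajectory step has a different fault. With Time 1 missing, two measurements can only be Time 0 and Time 2. In Arm B, Time 2 comes after the offer of the program, so a line through those points can place treatment gain in a value that is meant to represent the control condition.

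**Working it through.** **Inputs from the Protocol.** 60 per arm (Section 2.3); expected retention 85-90%, and previous-RCT retention 90.3% and 93.8% (Section 2.14). The pilot retention there reproduces: 19/22 = 86%. Of 120 enrolled, 85-90% is 102 to 108 families, so 12 to 18 would be lost. The Protocol gives no figure for the effect of its missing-data rule and no response rates, so the latter are assumed below.

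**1. Zero rule on the planned rate scale.** Let rA and rB be retention, and suppose that loss is unrelated to outcome and that lost families are given the same average offset as the others (a missing video has no prompt count, so some offset must be supplied). Each arm's Time 1 rate is multiplied by its retention and Time 0 is untouched, so

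rate ratio after the rule = true rate ratio × rA / rB.

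| Retention A / B | Multiplier |
|---|---|
| 85% / 90% | 0.85/0.90 = 0.944 |
| 90% / 85% | 0.90/0.85 = 1.059 |
| 90.3% / 93.8% (previous RCT) | 0.903/0.938 = 0.963 |

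No response rate is needed for these.

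**2. Is it a lower bound?** The outcome is a proportion, so the least favourable filling for the comparison is 0 for missing Arm A values and 1 for missing Arm B values. Assume Time 1 rates of 0.45 (A) and 0.30 (B), a true difference of 0.150, with 10% lost in A and 15% in B:
- Zero rule: 0.90 × 0.45 − 0.85 × 0.30 = 0.405 − 0.255 = 0.150, with ratio 0.405/0.255 = 1.59 against a true 1.50.
- Least favourable filling: 0.405 − (0.255 + 0.15 × 1) = 0.000.

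Here the zero rule leaves the difference intact and raises the ratio, while the true bound is no difference at all.

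**3. Size under no true effect.** The bias on the difference scale is (loss B − loss A) × mean. With an assumed mean of 0.40:
- A 10%, B 15%: 0.05 × 0.40 = +0.020. This is 9 − 6 = 3 more families lost in Arm B: 3/60 × 0.40 = 0.020. Three lost in each arm would give zero.
- A 15%, B 10%: −0.020.
- Previous RCT, A 9.7%, B 6.2%: −0.035 × 0.40 = −0.014.

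Simulated error rates (60 per arm, mean 0.40, SD 0.20, correlation of Time 0 with Time 1 of 0.5, t-test on change, 20,000 replicates; nominal 2.5% per side):
- A 10%, B 15%: about 6.5% favouring treatment. The range is 5.6-7.8% over means of 0.30-0.50 with SDs of 0.15-0.25, and 5.5-6.3% with groups of 6 and intraclass correlation of 0.02-0.10.
- A 15%, B 10%: about 6.5% against treatment.
- Previous RCT pattern: 1.0% favouring and 5.0% against treatment.

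With equal loss there is no bias under the null, but the added zeros raise the variance. For a true difference of 0.10, power at 10% loss in each arm was 53%, against 72% in completers. Part of that cost is specific to the difference scale, where equal loss also shrinks the effect; by step 1 the rate ratio is unchanged by equal loss.

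**4. Trajectory step.** Let m be the untreated mean, e the gain (kept to Time 2 in Arm A, reached by Time 2 in Arm B) and s the share of each arm missing Time 1 but seen at Time 2. With equal spacing, a straight line fills Time 1 with m + e/2 in both arms:

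A = (1 − s)(m + e) + s(m + e/2); B = (1 − s)m + s(m + e/2); A − B = (1 − s)e.

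At s = 5% this is 0.95e and at s = 10% it is 0.90e. Half of the loss, s × e/2, comes from program gain entering Arm B. With no gain in either period there is no bias. Both values of s are assumptions; the Protocol gives none.

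**The case against.** The case on the other side is substantial. The wording is permissive, and a separate analysis plan may make the zero rule a sensitivity analysis. An analysis of only the 100 completers targeted in Section 2.14 would never use it. The label is accurate for an individual child. The only arm-specific retention in the document points to more loss in Arm A, where the rule is conservative, and the later offer of the program gives controls a reason to stay. Loss at Time 1 may also be smaller than 10-15%: the previous RCT's figures are at 6 months, the pilot's 86% counts program completion, and Section 2.5 states that "all families will be invited to provide end-of-study data even if multiple sessions are missed". The reference list includes a paper on intention-to-treat analysis with missing outcomes that the available text does not cite, so related text may be absent.

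These points limit the size and certainty of the harm. They do not make the zero rule a bound on the comparison in either role, and the previous RCT tested an individual, in-person, 12-week program, so its loss pattern need not recur.

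A reader might infer something stronger. Section 2.1 describes "growth curve analysis of treatment group at" the three time points, and Section 2.9 has "Follow-up (treatment group only" as a heading. From these one could conclude that only Arm A is interpolated while comparable controls are set to zero, which would favour treatment even with equal loss. The documents do not support that. The imputation sentence in Section 2.16 applies to each participant without naming an arm, and Section 2.7 schedules Time 2 in both groups. The two treatment-group phrases describe a design component and a follow-up analysis, not the imputation rule.

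**Conclusion.** The concern holds in a limited form. The zero rule is worst-case for a toddler and not for the between-arm effect, which it can move either way: a factor of 0.944 to 1.059 on the rate ratio across the expected retention range, given loss unrelated to outcome and a comparable supplied offset. A difference of about three lost families between arms is enough to raise the one-sided error from 2.5% to about 6.5%, in whichever direction the imbalance runs. That error rate rests on assumed response rates and on a t-test in place of the count model. The trajectory step can only attenuate under the assumptions shown, by an amount the documents do not let one fix.

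It would be wrong to conclude that the plan will favour treatment, or that the zero rule is the primary analysis. The first depends on a loss pattern opposite to the only arm-specific one reported, and the second is not stated. The point deserves correction because the label would present a result as conservative when it may not be, and because the choice is left open until dropout is known.

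**What to change.** Base the primary analysis on the planned Poisson or negative binomial model, fitted to all available observations under missing-at-random, with time as a category and arm-by-time terms. No single-value zero and no individual-line imputation is then needed. Arm B's Time 2 has its own mean, so post-program data are not treated as lying on the control-phase trajectory.

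If zero imputation is kept, state that it is a sensitivity analysis, give the offset to be used for a missing video, and do not call it worst-case for the comparison. Set beside it an arm-specific delta or tipping-point analysis that gives unfavourable values to Arm A dropouts.

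The cost is analysis wording and a little programming; no new data are needed.
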